### **8.5 Treatment Discontinuation**

Patients should discontinue treatment but remain in the study for adequate follow-up, for any of the following reasons:

- Patients may discontinue study drug treatment at any time if the patient, Investigator, or the Sponsor determines that it is not in the best interest of the subject to continue treatment.
- Unacceptable toxicity associated with treatment (see Study Treatment Arm Stopping Rule section for details).
- Clinically significant lab abnormalities or AEs that, in the Investigator's judgment, would preclude continued treatment.

The reason for treatment discontinuation will be noted on the e-CRF, reported to the Sponsor, and documented in the clinical study report.

If a patient discontinues treatment due to unacceptable toxicity or any other safety reason, that patient should continue to be assessed according to the planned visit schedule for safety, or at the minimum, attend a Treatment Discontinuation Visit four (4) weeks after having received the last dose of study drug.

A clear distinction should be made between study withdrawal and treatment discontinuation.

### **8.6 Replacement of Patients**

A subject who withdraws during the pretrial evaluations but before receiving the treatment will not be considered as a drop-out and will not be included in the final statistical analysis.

Standbys should be recruited and available to replace any subject who withdraws prior to the first treatment administration.

Patients who are withdrawn or lost to follow-up during the study may be replaced in order to achieve the number of evaluable patients required, per the sample size calculations, to address the primary objective.

## 9. STUDY CONDUCT

### 9.1 Timing of Assessments

All scheduled clinic visits allow a +/- 1 day window. See Section 2 for the Schedule of Activities. The latest version of the consent form must be signed prior to subject's inclusion (prior to initiating any protocol procedure).

### 9.2 Study Visits and Procedures

Prior to any study specific screening activities, all potential patients will sign the Study Informed Consent Form (ICF). The consent forms will comply with all applicable regulations governing the protection of human subjects. An ICF, approved by the Sponsor and the site's institutional review board (IRB) or Ethics Committee (EC), must be used. The consent form can be signed up to 28 days before screening visit.

#### 9.2.1 Screening and Eligibility Assessments (Visit 1, Day -15)

On Day -15 prior to randomization, interested SBS patients will undergo a screening session, Visit 1. Patients will arrive in the fasted state (i.e. fast for 4 hours before visit). This visit is comprised of the following elements:

1. Verification of identity and demographics (age, gender, race);
2. Confirmation of the SBS diagnosis will be obtained, with proper medical history data;
3. Description of the type and extent of intestinal surgical resection will be provided (if applicable);
4. Verification of all inclusion and exclusion criteria;
5. Collection of medical history including history of intestinal surgical resection or other possible cause of SBS, all current medications and therapies, non-prescription drug intake, and HPN if still administered. Particular attention will be paid to obtaining the history of diarrhea in the 3 months prior to screening, as well as prohibited drugs;
6. Measurement of body weight and height, and calculation of BMI;
7. Measurement of vital signs including heart rate, blood pressure and body temperature;
8. Complete physical examination;
9. An ECG will be performed;
10. All safety laboratory tests including hematology, serum chemistry, pregnancy test (if applicable) and urinalysis (dipstick). Screening laboratory results must be available and reviewed by the Investigator before randomization.
11. Patients will be given a bowel movement (BM) and BSFS diary, in which they will need to record daily the number of stools and their form, using the BSFS. Proper instructions will be provided for the use of the BSFS. Patients will be instructed to start recording in this Screening diary at Day -14 and to fill it out daily until Day -1 inclusive, in order to establish a baseline and confirm patients' eligibility.
12. All screening results must be available prior to Day 0 randomization so that the study Investigator can determine eligibility.
13. From screening to the first dose of the study, AEs will be recorded as screening events or as part of the medical history, as applicable.

#### 9.2.2 Screening Telephone Contact (Phone 1, Day -8)

Each patient will be contacted by phone by the study coordinator, to inquire about the occurrence of AEs, any changes in medications, and use of the BM and BSFS screening diary.

### 9.2.3 Randomization (Visit 2, Day 0)

Eligible SBS patients will be invited to the study site for the selected baseline procedures.

1. Verification of completion of the BM and BSFS screening diary and review of eligibility criteria to decide if patient can continue to be randomized into the study. If yes:
2. Vital signs will be measured (heart rate, blood pressure and body temperature).
3. A urine pregnancy test will be performed if applicable. This test must be negative to dispense study medication.
4. Randomized patients will receive a 14-day supply of study treatment. Patients will be instructed to start taking their study medication the next day in the morning, i.e. on Day 1, and for 14 consecutive days, until Day 14 inclusive.
5. Patients will be given a new BM and BSFS diary for Period 1, in which they will need to record daily the number of stools and their form, using the BSFS, for Days 1 to 14 inclusive. Proper instructions will be provided for the use of the BSFS. They will also be provided the BM/BSFS diary for the Washout period, to be completed during Days 15 to 28.
6. Patients will be given a VAS questionnaire to complete on site. The four 11-point VAS scales (from 0 to 10), will be used by the patients to make an overall assessment of diarrhea, abdominal pain, bloating and urgency experienced during the last 24 hours. Zero will mean no symptom at all, and 10: very severe. The VAS assessments will be made at Days 0, 15, 28 and 43, but not during screening.

### 9.2.4 Period 1 Telephone Contact (Phone 2, Day 7)

Each patient will be contacted by phone by the study coordinator, to inquire about the occurrence of AEs, concomitant medications, compliance to study treatment and use of the BM and BSFS diary.

### 9.2.5 Washout (Visit 3, Day 15)

On the first day of the Washout period (**Day 15**), patients will return to the clinic with their BM and BSFS diaries, and the remaining study medication. Patients will arrive in the fasted state (i.e. fast for 4 hours before visit). The following assessments and procedures will be performed:

1. Complete physical examination;
2. Measurement of vital signs including heart rate, blood pressure and body temperature;
3. Measurement of body weight, and calculation of BMI;
4. All safety laboratory tests, including: urinalysis (dipstick), hematology, serum chemistry;
5. Recording of concomitant medications;
6. Study drug compliance check – patients will return all study medication from Period 1 to the study coordinator. Drug accountability will be performed.
7. Verification of completion of the BM and BSFS diary for Period 1, and start of diary for Washout. Patients will return the Period 1 diary and will be reminded to complete the Washout diary daily during Days 15 to 28.
8. The VAS symptoms questionnaire will be completed by the patient on site.
9. Recording of AEs and concomitant medications.

During the Washout period (**Days 15 – 28**), patients will not be taking any study medication, for 14 consecutive days. Other concomitant medications can be maintained as long as their dose and dosing regimen remain unchanged (See

Permitted Medications section for details). Patients will be instructed to keep using their BM/BSFS diary during the washout period to report the daily number of bowel movements as well as stool form using the BSFS.

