## 2. SCHEDULE OF ACTIVITIES

All scheduled clinic visits and telephone contacts allow a +/- 1 day window.

	Screening and Study Start (Days -15 to 0)			Period 1 (Days 1 to 14)	Washout (Days 15 to 28)			Period 2 (Days 29 to 42)	End of Study (Day 43)
Days	-15	-8	0	7	15	21	28	35	43
Visits	Visit 1	Phone 1 	Visit 2	Phone 2 	Visit 3	Phone 3 	Visit 4	Phone 4 	Visit 5
Informed Consent 	X								
Eligibility criteria review	X		X						
Demographics	X								
Medical History	X								
Randomization (to sequence)			X						
Vital signs 	X		X		X		X		X
Phys. Exam., Body Weight, Height (Day -15 only), BMI	X				X		X		X
Clinical Laboratory Tests 	X				X		X		X
Urinalysis 	X				X		X		X
12-lead ECG	X								X
Pregnancy Test (females only)	X (serum)		X (urine)				X (urine)		X (urine)
Study Drug Dispensing			X				X		
Compliance check (study drug accountability)					X				X
BSFS and BM diary 	X	X	X	X	X	X	X	X	X
Visual Analog Scale (symptoms) 			X		X		X		X
Concomitant Medication 	X	X	X	X	X	X	X	X	X
AE Monitoring 	X	X	X	X	X	X	X	X	X

-  The latest version of the consent form must be signed prior to subject's inclusion (prior to initiating any protocol procedure). The consent form can be signed up to 28 days before screening visit.
-  Vital signs include pulse, blood pressure (diastolic-systolic) and body temperature.
-  Clinical Laboratory safety tests include full clinical chemistry and hematology panels.
-  Urinalysis includes nitrites, urobilinogen, protein, pH, blood, specific gravity, ketones, bilirubin, leukocytes, glucose and appearance.
-  BSFS: Bristol Stool Form Scale BM: bowel movement (defecation). Patients will use the 14-day diaries to record the frequency of BMs as well as stool morphology, throughout the study (ie. Diaries will be provided for Screening, Period 1, Washout and Period 2).
-  Telephone contact will be established with patients at Days -8, 7, 21 and 35, to assess safety, report concomitant medication use, promote use of diary, and promote compliance.
-  An 11-point Visual Analog Scale (VAS) will be used to assess the following symptoms: abdominal pain, diarrhea, bloating and urgency

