#### **9.2.7 Washout (Visit 4, Day 28)**

On the last day of the Washout period (**Day 28**), patients will return to the clinical with their BM/BSFS diary. Patients will arrive in the fasted state (i.e. fast for 4 hours before visit). The following assessments and procedures will be performed:

1. Complete physical examination;
2. Measurement of vital signs including heart rate, blood pressure and body temperature;
3. Measurement of body weight, and calculation of BMI;
4. All safety laboratory tests, including at a minimum: urinalysis (dipstick), hematology, serum chemistry;
5. A urine pregnancy test will be performed if applicable. This test must be negative to dispense study medication for Period 2.
6. Recording of concomitant medications;
7. Verification of the BM and BSFS Washout diary. The Washout diary will be given back to the patient and they will be instructed to continue using the diary for Day 28. The patient will also be provided a new diary for Period 2.
8. The VAS symptoms questionnaire will be completed by the patient on site.
9. Recording of AEs;
10. Study medication for Period 2 will be supplied at the end of the visit, with instructions to begin dosing on Day 29.

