#### **9.2.9 End-of-Study (Day 43, Visit 5)**

At Day 43, the final clinic visit, all patients will return to the clinic with their BM and BSFS diaries, and the remaining study medication. Patients will arrive in the fasted state (i.e. fast for 4 hours before visit). The following assessments and procedures will be performed:

1. Complete physical examination;
2. Measurement of vital signs including heart rate, blood pressure and body temperature;
3. Measurement of body weight, and calculation of BMI;
4. A 12-lead ECG;
5. All safety laboratory tests, including at a minimum: urinalysis (dipstick), hematology, serum chemistry;
6. A urine pregnancy test will be performed if applicable;
7. Recording of concomitant medications;

8. Study drug compliance check - patients will return all study medication from Period 2 to the study coordinator. Drug accountability will be performed.
9. Verification of completion of the BM and BSFS diaries for Washout and for Period 2. The diaries will be given back to the study coordinator.
10. The VAS symptoms questionnaire will be completed by the patient on site.
11. Recording of AEs.

AEs still ongoing at the time of the visit will be assessed and evaluated for further follow-up as necessary. SAEs occurring during the 30-day period following the End-of-Study, Day 43 visit, should be reported to the medical monitor. (See Serious Adverse Event Reporting section for details)

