**APPENDIX 1: Sample Bowel Movement and BSFS Diary**

**Daily Symptom and Stool Diary – Period 1**

DAY	DATE (e.g. Monday 05/Jun/18)	Loperamide taken today (e.g. 2 pills)	Time Study Drug Taken (24 hr clock)	STOOL FORM AND TIME (Stool Form = 1 to 7 from chart below; Time = time of stool, 24 hour clock (e.g. 15:30 for 3:30 pm))												
				1 st	2 nd	3 rd	4 th	5 th	6 th	7 th	8 th	9 th	10 th	11 th	12 th	
1				Form												
				Time												
2				Form												
				Time												
3				Form												
				Time												
4				Form												
				Time												
5				Form												
				Time												
6				Form												
				Time												
7				Form												
				Time												

1  Separate hard lumps, like nuts	4  Like a sausage or snake, smooth and soft	7  Watery, no solid pieces
2  Sausage shaped but lumpy	5  Soft blobs with clear cut edges	
3  Like a sausage or snake, but with cracks on its surface	6  Fluffy pieces with ragged edges, a mushy stool

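### The ±1 day window allows Visits 3 and 5 on Day 14 and Day 42, when diary and drug are collected before the primary-endpoint week is over

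*Combined protocol and SAP*

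**What the plan says.** The primary endpoint is the change in weekly bowel movements from baseline to the second treatment week, Days 8 to 14 and Days 36 to 42 (Section 7.1.1).

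The window is stated twice, without exception for any visit. Section 2: "All scheduled clinic visits and telephone contacts allow a +/- 1 day window". Section 9.1: "All scheduled clinic visits allow a +/- 1 day window".

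Diary and drug are handled as follows.

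- **Visit 2 (Section 9.2.3, items 4 and 5).** Dosing and the Period 1 diary both run through Day 14 inclusive. For the Washout diary: "They will also be provided the BM/BSFS diary for the Washout period, to be completed during Days 15 to 28".
- **Visit 3, Day 15 (Section 9.2.5, items 6 and 7).** All Period 1 drug comes back. For the diaries: "Patients will return the Period 1 diary and will be reminded to complete the Washout diary daily during Days 15 to 28".
- **Visit 4, Day 28 (Section 9.2.7, item 7).** This visit is scheduled on a diary day, and the protocol provides for it: "The Washout diary will be given back to the patient and they will be instructed to continue using the diary for Day 28".
- **Visit 5, Day 43 (Section 9.2.9, items 8 and 9).** All Period 2 drug comes back, and for the Washout and Period 2 diaries: "The diaries will be given back to the study coordinator".

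Section 11 fixes each period or treatment cycle at 14 calendar days whatever the visit windows. Section 12.1 asks for daily recording up to Day 42.

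**The concern.** A visit held one day early is within the window, yet it takes the diary away during the last day of the endpoint week. Stools later that day then have no assigned place. At Visit 3 the patient does hold another diary, but it is assigned to Days 15 to 28. After Visit 5 the patient holds none. Checking the diary for completeness at the visit cannot add stools that have not yet happened.

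If the shortened day is counted as a full one, the week-2 total is too low and the fall from baseline looks larger than it was. The error at these two visits can only go in that direction. Steps (a) and (b) of Section 14.6.1 test each dose against baseline with no placebo period, so nothing in those tests offsets it.

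The same visit also collects the remaining drug, so the evening dose of Day 14 or Day 42 may be lost. That is one of the 2 × 14 = 28 planned doses in the period.

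**Working it through.** **The plan's own figure.** Section 14.1 assumes an SD of change of 2.0 for each dose and a correlation of 0.80 between doses. The SD of the difference is √(4 + 4 − 2 × 0.80 × 4) = √1.6 = 1.265, as stated. A two-sided paired t-test at 0.05 for a difference of 1.00 then needs 15 patients (power 81.2%), which matches Table 3, and 15 × 1.2 = 18. This is not in dispute.

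**Which days an early visit can hit.** Visit 3: Day 15 − 1 = Day 14, the last of Days 8 to 14. Visit 5: Day 43 − 1 = Day 42, the last of Days 36 to 42.

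**Stools at risk in an affected patient and period.** Inputs from the documents are the entry minimum of about 3 stools a day (inclusion criterion 10) and the assumed fall of 4 a week (Section 14.1). The visit time and the spread of stools over the day are my assumptions.

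- On-treatment frequency: 3 × 7 − 4 = 17 a week, and 17 / 7 = 2.43 a day.
- Stools missed = 2.43 × share of the day left after the visit.

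| Visit time | Stools spread over 24 h: share left, stools missed | Stools spread over 07:00–23:00: share left, stools missed |
|---|---|---|
| 09:00 | 0.625, 1.52 | 0.875, 2.13 |
| 11:00 | 0.542, 1.32 | 0.75, 1.82 |
| 15:00 | 0.375, 0.91 | 0.50, 1.21 |

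The range is 0.9 to 2.1 stools, or 0.91 / 17 = 5% to 2.13 / 17 = 12.5% of that week's total. A patient whose true fall is 4 would be recorded with a fall of 4.9 to 6.1. Patients with more frequent stools lose more: at 4 a day before treatment, (28 − 4) / 7 = 3.43 a day on treatment, and a visit with half the day left misses 1.7.

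**Trial level, for illustration only.** One affected patient among 15 raises that dose's mean fall by 0.91 / 15 = 0.06 to 2.13 / 15 = 0.14 stools a week. In general the shift is the early-visit rate times the stools missed. The documents give no rate, so these are assumed:

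- 5% early, 0.9 missed: 0.05 × 0.9 = 0.045
- 10% early, 1.3 missed: 0.10 × 1.3 = 0.13, about 3% of the assumed fall of 4
- 20% early, 2.1 missed: 0.20 × 2.1 = 0.42, about 10% of the assumed fall of 4

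At a true fall of 4 with SD 2 and 15 patients, each dose-versus-baseline test already has more than 99.9% power. The shift could therefore change a conclusion only if the true effect were close to zero. In the between-dose comparison the mean shift cancels if early visits are equally common under both doses.

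**The case against.** The strongest reply is that the specific instructions point against a Day 14 visit. Section 9.2.5 names Day 15, Section 11 holds the cycle at 14 days regardless of windows, and Section 12.1 asks for recording to Day 42. A careful site would see the conflict and avoid the early date. That stands as a reason to expect few such visits. It does not remove them: the window covers every clinic visit without exception, and none of these passages narrows it or leaves the diary with the patient.

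Other safeguards are partial.

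- At Visit 3 the patient already holds the Washout diary and could write late Day 14 stools in it. The sample diary in Appendix 1 has dates and clock times, so a shortened day can be recognised, and Section 17 provides for queries on missing data. None of this helps after Visit 5 unless the patient reconstructs the day from memory.
- A patient who hands in drug before the last evening dose has not taken everything dispensed and so falls outside the per-protocol population (Section 14.2). That protects the secondary analysis, at the price of losing a patient through a permitted visit date. The primary analysis is ITT.
- Section 14.6.1 has no rule for a shortened day, but Section 14 leaves analysis detail to a SAP that is not among the documents supplied. Silence in the protocol does not show that no rule exists.

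Two stronger readings are tempting and are not supported. A reader might infer that an early Visit 2 shortens the baseline week and so partly offsets the error, because the screening diary is to be filled in by instruction to "fill it out daily until Day -1 inclusive". But Section 12.1 ties baseline to the week before randomization, and Section 9.2.3 starts drug the day after Visit 2. An early Visit 2 shortens the 14-day screening diary by a day and still leaves seven complete days before randomization.

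A reader might also infer a real loss of between-dose power. With 15 completers, 10% early visits and 1.3 stools missed each time, power for a difference of 1.00 is 81% if the same patients are early in both periods and 74% if early visits are independent across periods. The result follows from a rate and a correlation that the documents do not give, so it is no evidence of an underpowered trial.

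**Conclusion.** The point holds as a gap in visit timing. The protocol permits Visits 3 and 5 on the last day of a primary-endpoint week and collects both diary and drug at those visits, against its own instructions to dose and record through that day. The hand-back step that covers this situation at Visit 4 is missing at the two visits that close the endpoint weeks.

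For an affected patient and period the loss is about 1 to 2 stools, always in the direction of benefit, and possibly one dose. This assumes the entry-minimum frequency, the planned fall of 4 a week, and a visit between mid-morning and mid-afternoon. The effect on the trial result depends on an unknown early-visit rate and is probably small. The change is worth making because it is cheap, not because the result is in danger. Confidence is medium.

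**What to change.** In Section 2 and Section 9.1, state that the window for Visits 3 and 5 is 0/+1 day, so that neither can be held before Day 15 or Day 43. The other visits keep ±1 day. This removes the loss of stools and of the evening dose from this cause, and the sample size stays at 18.

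Copying the Visit 4 hand-back step would be a weaker remedy. It would keep the diary with the patient but not the drug, and after Visit 5 there is no later visit at which to collect the diary.

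The cost is one day less scheduling flexibility at two visits. Some visits that would have been early may move to Day 16 or Day 44, where the 24-hour VAS recall (Section 12.3) covers mostly time off drug. The present window already allows those dates. No patients, visits or procedures are added.

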#### **9.2.6 Washout Telephone Contact (Phone 3, Day 21)**

Each patient will be contacted by phone by the study coordinator, to inquire about the occurrence of AEs, concomitant medications, compliance to study treatment and use of the BM and BSFS diary.

#### **9.2.7 Washout (Visit 4, Day 28)**

On the last day of the Washout period (**Day 28**), patients will return to the clinical with their BM/BSFS diary. Patients will arrive in the fasted state (i.e. fast for 4 hours before visit). The following assessments and procedures will be performed:

1. Complete physical examination;
2. Measurement of vital signs including heart rate, blood pressure and body temperature;
3. Measurement of body weight, and calculation of BMI;
4. All safety laboratory tests, including at a minimum: urinalysis (dipstick), hematology, serum chemistry;
5. A urine pregnancy test will be performed if applicable. This test must be negative to dispense study medication for Period 2.
6. Recording of concomitant medications;
7. Verification of the BM and BSFS Washout diary. The Washout diary will be given back to the patient and they will be instructed to continue using the diary for Day 28. The patient will also be provided a new diary for Period 2.
8. The VAS symptoms questionnaire will be completed by the patient on site.
9. Recording of AEs;
10. Study medication for Period 2 will be supplied at the end of the visit, with instructions to begin dosing on Day 29.

